6.2 Preparation/Handling/Storage/Accountability

6.2.1 Dose Preparation

Details on preparation and administration of pembrolizumab are provided in the Pharmacy Manual. Cisplatin will be prepared and administered as per the approved product label(s).

6.2.2 Handling, Storage, and Accountability

The investigator or designee must confirm appropriate temperature conditions have been maintained during transit for all study intervention received, and any discrepancies are reported and resolved before use of the study intervention.

Only participants enrolled in the study may receive study intervention, and only authorized site staff may supply or administer study intervention. All study interventions must be stored in a secure, environmentally controlled, and monitored (manual or automated) area in accordance with the labeled storage conditions with access limited to the investigator and authorized site staff.

The investigator, institution, or the head of the medical institution (where applicable) is responsible for study intervention accountability, reconciliation, and record maintenance (ie, receipt, reconciliation, and final disposition records).

For all study sites, the local country Sponsor personnel or designee will provide appropriate documentation that must be completed for drug accountability and return, or local discard and destruction if appropriate. Where local discard and destruction is appropriate, the investigator is responsible for ensuring that a local discard/destruction procedure is documented.

The study site is responsible for recording the lot number, manufacturer, and expiry date for any locally purchased product (if applicable) as per local guidelines unless otherwise instructed by the Sponsor.

The investigator shall take responsibility for and shall take all steps to maintain appropriate records and ensure appropriate supply, storage, handling, distribution, and usage of study interventions in accordance with the protocol and any applicable laws and regulations.

6.3 Measures to Minimize Bias: Randomization and Blinding

6.3.1 Intervention Assignment

Intervention randomization will occur centrally using an IRT system. There are 2 study intervention arms. Participants will be assigned randomly in a 1:1 ratio to CCRT + pembrolizumab or CCRT + placebo, respectively.

6.3.2 Stratification

Intervention allocation/randomization will be stratified according to the following factors:

1. Planned type of EBRT: IMRT or VMAT versus non-IMRT and non-VMAT
2. Stage at screening of cervical cancer: FIGO 2014 Stage IB2-IIIB (node-positive disease) versus FIGO 2014 Stage III-IVA (node-negative or node-positive disease)
3. Planned total radiotherapy dose (EBRT + brachytherapy dose) of <70 Gy (EQ2D) versus \geq 70 Gy (EQ2D)

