Overall Design:

| | |
|-----------------------------|--|
| Study Phase | Phase 3 |
| Primary Purpose | Treatment |
| Indication | High-risk locally advanced cervical cancer |
| Population | Women with International Federation of Gynecology and Obstetrics 2014 Stage IB2-IIIB (with node-positive disease) and Stage III-IVA (either node-positive or node-negative disease) cervical cancer |
| Study Type | Interventional |
| Intervention Model | Parallel This is a multi-site study. |
| Type of Control | Placebo |
| Study Blinding | Double-blind with in-house blinding |
| Blinding Roles | Participants or Subjects Investigator Sponsor |
| Estimated Duration of Study | 
The Sponsor estimates that the study will require approximately 63 months from the time the first participant (or their legally acceptable representative) provides documented informed consent until the last participant's last study-related contact.
 
Extension Portion of the Study in China: The study may remain open longer than 63 months to complete an extension portion of the study in China.
 |

Number of Participants:

Approximately 980 participants will be randomized as described in Section 9.9.

Intervention Groups and Duration:

| Intervention Groups | Intervention Group Name | Drug | Dose Strength | Dose Frequency | Route of Administration | Regimen/ Treatment Period | Use |
|---|---------------------------|---------------------------|---------------------------|--|--|---------------------------|----------------------|
| Arm 1 | Pembrolizumab | 200 mg | Q3W | IV | 5 infusions | Test Product | |
| | | 400 mg | Q6W | IV | 15 infusions | Test Product | |
| Arm 2 | Placebo | 0 mg | Q3W | IV | 5 infusions | Placebo | |
| | | 0 mg | Q6W | IV | 15 infusions | Placebo | |
| For both Arm 1 and Arm 2 | Cisplatin | 40 mg/m ² | Once weekly | IV | 5 infusions (An optional, sixth infusion may be administered according to local practice) | | Background Treatment |
| For both Arm 1 and Arm 2 | Radiation (EBRT) | Refer to Radiation Manual | Refer to Radiation Manual | External radiotherapy (IMRT or VMAT /non-IMRT and non-VMAT) to primary tumor and nodal volumes | Within 40 days | | Background Treatment |

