2 INTRODUCTION

Cervical cancer is one of the most frequently diagnosed malignancies and causes of cancer related death among women [Bray, F., et al 2018]. Worldwide, there are an estimated 569,847 newly diagnosed cases of cervical cancer and an estimated 311,365 deaths per year [Bray, F., et al 2018]. The extent of disease at the time of diagnosis is a significant prognostic factor presenting patients with more advanced disease especially in developing countries [Pisani, P., et al 1999]. Women with LACC (Stage IB2 to IVA) have higher disease recurrence rates than those with earlier stages of disease.

According to FIGO 2014 staging, Stage IB2 is confined to the cervix with a clinically visible mass >4 cm, Stage II invades beyond uterus but not to pelvic wall or to the lower third of the vagina, Stage III extends to the pelvic sidewall and/or involves the lower third of the vagina, and/or causes hydronephrosis, or a nonfunctioning kidney, while Stage IVA invades the mucosa of the bladder or rectum, and extends beyond the true pelvis [Belhadj, H., et al 2014].

Rate of recurrence worsen by stage, and benefits of SOC treatment are greater with earlier versus more advanced stages of disease. The 5-year OS rates for Stage III to IVA versus Stage IB2 to IIB were reported as 60% versus 86%, respectively, demonstrating the impact of staging on prognosis [Cetina, L., et al 2006]. A meta-analysis from 18 randomized studies also provides clear evidence of a larger unmet medical need for patients with Stage III-IVA despite standard of care treatment [Chemoradiotherapy for Cervical Cancer Meta-Analysis Collaboratio 2008]. Most recently, patients with OS and pelvic control rates at 3 and 5 years were reported in a large, multicentral study clearly demonstrating worse control rates and survival for Stage III and IVA patients [Sturdza, A., et al 2016].

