4 STUDY DESIGN

4.1 Overall Design

This is a randomized, Phase 3, placebo-controlled, multisite, double-blind study of chemoradiotherapy with or without pembrolizumab in participants with high-risk LACC.

Approximately 980 participants will be enrolled in the global portion of the study. After enrollment of the global portion of the study is complete, the study may remain open to enrollment in China alone until the target number of participants in China has been enrolled to meet local regulatory requirements. An extension portion of the study will be identical to the global study, (eg, inclusion and exclusion criteria, study endpoints, primary and secondary objectives, study procedures, and statistical analyses).

Eligible participants with high-risk LACC FIGO 2014 Stage IB2-IIB (with node-positive disease) or Stage III-IVA (either node-positive or node-negative disease) will be randomly assigned in a 1:1 ratio to one of the following treatment arms:

- 1) Concurrent chemoradiotherapy in combination with pembrolizumab (200 mg Q3W for 5 infusions) followed by pembrolizumab alone (400 mg Q6W for 15 infusions) or
- 2) Concurrent chemoradiotherapy in combination with placebo (Q3W for 5 infusions) followed by placebo alone (Q6W for 15 infusions).

Standard of care CCRT is given during the Q3W dosing period of pembrolizumab (Arm 1) or placebo (Arm 2) and includes the following:

- 1) Cisplatin, 5 infusions given IV QW at 40 mg/m² (an optional, sixth infusion of cisplatin may be administered according to local practice) plus

- 2) EBRT over 40 days, followed by
- 3) Brachytherapy

Note: brachytherapy should follow the completion of EBRT, and the overall treatment time of EBRT and brachytherapy together should not exceed 50 days (with an extension to a maximum of 56 days for unforeseen delays). The minimum acceptable radiation is 80 Gy for volume-directed and 75 Gy for point-directed. Please refer to the Radiation Manual for further guidance.

Geographic variance in total radiation dose administered, number of fractions and methodology of application may be permitted after consultation with the Sponsor.

The SOC will be at least 3D conformal planning.

To limit overall treatment time, efficient organization of the whole multimodal treatment is required. This includes use of SIB in participants with lymph node involvement, minimizing treatment interruptions as much as possible and by planning the timing of brachytherapy carefully.

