5.1 Inclusion Criteria

A participant will be eligible for inclusion in the study if the participant:

Type of Participant and Disease Characteristics

1. Has high-risk LACC (a or b below):

- a. FIGO 2014 Stage IB2-IIIB (with node-positive disease) – must meet criteria below for positive pelvic lymph node OR para-aortic lymph node involvement up to the L1 cephalad body level.
 - Pelvic lymph node involvement as assessed by one of the following criteria:
 - Histopathologic, biopsy-proven pelvic node involvement (high-risk LACC patient with locally evaluable disease is eligible if removal of positive lymph node[s] is documented), or
 - 2 or more positive pelvic nodes by MRI or CT (≥ 1.5 cm shortest dimension), or
 - 2 or more positive pelvic nodes by PET / CT with SUV (max) ≥ 2.5

- Para-aortic lymph node involvement as assessed by one of the following criteria:
 - Histopathologic, biopsy-proven para-aortic node involvement (high-risk LACC patient with locally evaluable disease is eligible if removal of positive lymph node[s] is documented), or
 - 1 or more positive para-aortic nodes by MRI or CT (≥ 1.5 cm shortest dimension), or
 - 1 or more positive para-aortic nodes by PET / CT with SUV (max) ≥ 2.5

b. FIGO 2014 Stages III-IVA (either node-positive or node-negative disease)

Refer to Appendix 9 for further details of FIGO 2014 staging for cervical cancer.

2. Has histologically-confirmed squamous cell carcinoma, adenocarcinoma, or adenosquamous carcinoma of the cervix.
3. Has not previously received any definitive surgical, radiation, or systemic therapy for cervical cancer, including investigational agents, and is immunotherapy-naïve. Note: Previous surgical procedure for localized cervical tumor is allowed.
4. Has an ECOG performance status of 0 or 1 within 7 days prior to the first dose of study intervention.

Demographics

5. Is female, at least 18 years of age at the time of documented informed consent.

Female Participants

6. A female participant is eligible to participate if she is not pregnant or breastfeeding, and at least one of the following conditions applies:
 - Is not a WOCBP

OR

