Additional Categories

8. Has radiographically evaluable disease, either measurable or nonmeasurable per RECIST 1.1, as assessed by the local site investigator/radiology.
 - As per inclusion criterion #1, for Stage IB2-IIB (FIGO 2014) disease, if nodal involvement is assessed by CT or MRI, the participant must have measurable disease (≥ 1.5 cm in shortest dimension) per RECIST 1.1.
 - High-risk LACC patient with radiographically locally evaluable disease is eligible if removal of positive lymph node(s) is documented.

9. Has provided a tissue sample from a core, incisional, or excisional biopsy of a tumor to the central vendor prior to randomization. Formalin-fixed, paraffin-embedded tissue blocks are preferred to slides (details pertaining to tumor tissue submission can be found in the Laboratory Manual).
10. Has adequate organ function as defined in the following table (Table 2). Specimens must be collected within 7 days prior to the start of study intervention.

Table 2 Adequate Organ Function Laboratory Values

| System | Laboratory Value |
|--|---|
| Hematological | |
| Absolute neutrophil count (ANC) | $\geq 1500/\mu\text{L}$ |
| Platelets | $\geq 100\,000/\mu\text{L}$ |
| Hemoglobin | $\geq 9.0\text{ g/dL}$ or $\geq 5.6\text{ mmol/L}^a$ |
| Renal | |
| Measured or calculated ^b creatinine clearance | $\geq 50\text{ mL/min}$ |
| OR | |
| GFR | $\geq 50\text{ mL/min}/1.73\text{m}^2$ |
| Hepatic | |
| Total bilirubin | $\leq 1.5 \times \text{ULN}$ OR direct bilirubin $\leq \text{ULN}$ for participants with total bilirubin levels $>1.5 \times \text{ULN}$ |
| AST (SGOT) and ALT (SGPT) | $\leq 2.5 \times \text{ULN}$ |
| Coagulation | |
| International normalized ratio (INR) OR prothrombin time (PT) | $\leq 1.5 \times \text{ULN}$ unless participant is receiving anticoagulant therapy as long as PT or PTT is within therapeutic range of intended use of anticoagulants |
| Activated partial thromboplastin time (aPTT) | |
| ALT (SGPT)=alanine aminotransferase (serum glutamic pyruvic transaminase); AST (SGOT)=aspartate aminotransferase (serum glutamic oxaloacetic transaminase); GFR=glomerular filtration rate; ULN=upper limit of normal. | |
| ^a Criteria must be met without erythropoietin dependency within last 2 weeks; administration of packed RBCs is allowed prior to randomization. | |
| ^b Creatinine clearance (CrCl) should be calculated per institutional standard. | |

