9.1 Statistical Analysis Plan Summary

Key elements of the statistical analysis plan are summarized below. The comprehensive plan is provided in Sections 9.2 through 9.12.

| | |
|-----------------------|---|
| Study Design Overview | A Randomized Phase 3, Double-Blind Study of Chemoradiotherapy With or Without Pembrolizumab for the Treatment of High-risk, Locally Advanced Cervical Cancer |
| Treatment Assignment | 
Approximately 980 participants will be randomized in a 1:1 ratio between 2 treatment arms:
 
Arm 1: CCRT + pembrolizumab Arm 2: CCRT + placebo
 
Stratification factors are as follows:
 
 Planned type of EBRT: IMRT or VMAT versus non-IMRT and non-VMAT Stage at screening of cervical cancer FIGO 2014 Stage IB2-IIIB (node-positive disease) versus FIGO 2014 Stage III-IV (node-negative or node-positive disease) Planned total radiotherapy dose (EBRT + brachytherapy dose) of <70 Gy versus ≥70 Gy (EQ2D) |

| | |
|---|--|
| Analysis Populations | 
Efficacy: ITT
 
The analysis population for ORR consists of all randomly assigned participants with measurable disease.
 
Safety: APaT
 |
| Primary Endpoints | 
 • PFS as assessed by investigator or by histopathologic confirmation of suspected disease progression as assessed by investigator • OS |

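### Do the two stage levels used for stratification overlap, leaving node-positive Stage III participants without a defined stratum?

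*Combined protocol and SAP*

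**What the plan says.** Four places end the lower stage group at IIIB:

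- Synopsis 1.1, study population: "2014 Stage IB2-IIIB (with node-positive disease) and Stage III-IVA (either node-positive or node-negative disease) cervical cancer".
- Section 5.1, criterion 1a: "FIGO 2014 Stage IB2-IIIB (with node-positive disease". Criterion 1b then admits "FIGO 2014 Stages III-IVA (either node-positive or node-negative disease".
- Section 6.3.2, stratification: "Stage at screening of cervical cancer: FIGO 2014 Stage IB2-IIIB (node-positive disease) versus FIGO 2014 Stage III-IVA (node-negative or node-positive disease".
- Section 9.1, SAP summary: "Stage at screening of cervical cancer FIGO 2014 Stage IB2-IIIB (node-positive disease) versus FIGO 2014 Stage III-IV (node-negative or node-positive disease". Here the second level also ends at IV instead of IVA.

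Three places end it at IIB:

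- Section 4.1, in the sentence that describes randomization: "Eligible participants with high-risk LACC FIGO 2014 Stage IB2-IIB (with node-positive disease) or Stage III-IVA".
- Section 5.1, criterion 8: "As per inclusion criterion #1, for Stage IB2-IIB (FIGO 2014) disease, if nodal involvement is assessed by CT or MRI".
- Section 2, Introduction: "The 5-year OS rates for Stage III to IVA versus Stage IB2 to IIB were reported as 60% versus 86%, respectively".

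Section 9.6.1.2 bases the OS log-rank test on the factors in 6.3.2. Section 9.6.1.5 applies the randomization factors to ORR. Section 9.6.1.1 and Table 9 specify a stratified log-rank test and a stratified Cox model for PFS.

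**The concern.** Strata should be mutually exclusive. If the lower level runs to IIIB and the upper level starts at III, node-positive IIIA and IIIB belong to both, and 6.3.2 gives no rule to choose between them. Because 6.3.2 defines strata for randomization and for the primary tests, an ambiguity there could have three effects:

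- sites or the interactive response system might assign similar participants to different strata;
- an outside analyst could not rebuild the stratified analysis from the protocol text;
- someone might choose, after seeing data, where node-positive Stage III belongs.

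The two stage groups differ in prognosis. The Introduction's 5-year OS figures of 60% and 86% imply, under exponential survival, a hazard ratio of ln(0.60)/ln(0.86) = 3.4. That is an upper bound here, since the 86% is not restricted to node-positive disease. Mixing the groups would therefore cost some precision.

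**Working it through.** **1. Which participants are ambiguous?** Take every FIGO 2014 stage in the eligible range (Appendix 9) by nodal status and assign it to the lower level (L) or upper level (U).

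| Stage | Nodes | L ends at IIIB | L ends at IIB |
|---|---|---|---|
| IB2, IIA1, IIA2, IIB | positive | L | L |
| IB2, IIA1, IIA2, IIB | negative | not eligible | not eligible |
| IIIA, IIIB | positive | **L and U** | U |
| IIIA, IIIB | negative | U | U |
| IVA | either | U | U |

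Two cells overlap under the IIIB wording: IIIA node-positive and IIIB node-positive. None overlaps under IIB. The set of eligible cells is the same in both columns, because criterion 1b admits all of Stage III whatever the nodal status.

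**2. Which reading is intended?**

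- Criterion 8 attributes the IIB range to criterion 1, so it is evidence of what criterion 1a was meant to say.
- With IIIB, the nodal requirement in 1a would do nothing for Stage III, because 1b already admits those participants. With IIB, each of 1a and 1b does separate work.
- The second level in 6.3.2 expressly covers Stage III of either nodal status. Node-positive Stage III is therefore named there, and putting those participants in the lower level would contradict it.
- Section 4.1 and the Introduction use the same split: up to IIB against III-IVA.

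**3. Does the ending at IV in Section 9.1 matter?** Exclusion criterion 2 removes Stage IVB, so among eligible participants III-IV and III-IVA are the same group.

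**4. Do the design figures depend on it?** Schoenfeld's formula with 1:1 allocation gives power = Φ(√D/2 × |ln HR| − 1.960).

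- PFS (Section 9.9: 304 events, HR 0.660): √304/2 × 0.4155 = 3.622. Then 3.622 − 1.960 = 1.662, so power is 95.2% (stated 95%).
- OS (240 events, HR 0.671): √240/2 × 0.3990 = 3.090. Then 3.090 − 1.960 = 1.130, so power is 87.1% for a single look. With O'Brien-Fleming spending and assumed interim counts of 120/180/240 or 150/200/240, it is about 86.2% to 86.5% (stated 86%; the planned OS interim counts are redacted).

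The stage wording enters neither figure.

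**5. What if the system really had been programmed with the overlap?** Treatment would still be randomized within whatever stratum was recorded. A log-rank test stratified by that recorded stratum therefore remains valid, and only efficiency is at risk. The documents give no stage distribution, so the size has to be illustrated under assumptions:

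- 980 participants, 55% Stage III-IVA, half of these node-positive, with IVA not separated out (980 × 0.55 × 0.50, about 270 participants);
- half or all of those 270 coded to the lower level;
- permuted blocks of 4, exponential times, two-year uniform accrual, a single look, stratification on stage only;
- Stage III-IVA 5-year OS of 60%, and 2-year PFS of 50% (the Introduction's statement that about half recur within 2 years).

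Power lost by analysing the coded rather than the true stage, in percentage points:

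| Stage hazard ratio | OS | PFS |
|---|---|---|
| 1.5 to 2.0 | 0.1 to 0.3 | 0.2 to 0.8 |
| 3.4 (upper bound) | 0.8 to 1.9 | 0.7 to 1.6 |

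Simulated one-sided type I error was 2.2% to 2.7% (nominal 2.5%). A smaller rerun under the same assumptions agreed within simulation error. This simulation leaves out the other two stratification factors and the interim looks, so it shows only the order of magnitude.

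**The case for a change.** The best argument for acting is that the correction is cheap and the definition is central. Both primary tests are stratified, the IIIB wording appears in four places, and a reader who takes 6.3.2 alone cannot rebuild the strata. Aligning the text, and stating that the stratum recorded at randomization is the one analysed, would close off a choice after unblinding. Four matching passages also make a single misread unlikely.

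Part of this stands: as printed, the levels do overlap, and consistent wording would be tidier. It does not amount to a defect in the plan.

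- The four passages share almost the same string, so a systematic misread could repeat. The same text shows stray letters elsewhere: the dechallenge label and the IRB/IEC abbreviation in Section 10.3.5 are both garbled, and Section 9.8.1.2 ends with a sentence foreign to a protocol. Against that, a similar string in 4.1 was read as IIB. Only the source PDF can settle it.
- Section 6.3.2 is not read alone. Section 4.1 and criterion 8 settle the intent.
- Analysing strata as randomized is ordinary practice. Section 9.6.1.5 already says so for ORR, and the PFS and OS method sections have redacted or missing material that may say the same.
- The harmful scenario needs a fault in the interactive response system, and the documents give no evidence of one.

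**Conclusion.** The concern does not call for a change. At most it is a one-letter clerical inconsistency, and it may not be in the source at all. The documents show the intended split to be IB2-IIB node-positive against III-IVA of any nodal status. Eligibility, alpha, event counts, sample size and the stated power are untouched.

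If the overlap had been carried into randomization, validity would hold. The loss would be under one percentage point of power at stage hazard ratios of 1.5 to 2.0, and about two points at the extreme of 3.4. Those sizes rest on an assumed stage and nodal mix and on a coding fault that nobody has shown.

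The conclusion assumes that the randomization system used the non-overlapping levels and that the analysis uses the recorded stratum. Both are normal practice, and a look at the source PDF and the system specification would confirm the wording and the levels without amending anything.

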6.3.3 Blinding

A double-blinding technique with in-house blinding will be used. The participant, the investigator, and Sponsor personnel or delegate(s) who are involved in the study intervention administration or clinical evaluation of the participants are unaware of the intervention assignments.

